This proposal extends the use of auditory and cognitive predictors to examining individual differences in the ability to track and understand a target speaker in competing noise. In addition to the direct effects of auditory resolution and working memory on recognition of target speech, we propose that auditory resolution and cognitive factors also indirectly affect speech recognition in competing speech by determining the listener’s ability to segregate target speech from competing sound sources. Competing speech can act in two ways: it can overlap with target speech and mask portions of the target which provide speech information (“energetic” masking), and it can intrude on the listener’s processing of the target speech information (“informational” masking) (Kidd et al. 2008; Shinn-Cunningham and Best 2008). Individuals with normal hearing can rely on auditory cues, such as voice pitch, to help separate target and masking speech from one another, but individuals with cochlear implants have difficulty hearing voice pitch differences (Chatterjee and Peng 2008; Deroche et al. 2014) and need large differences between target and masker voices to recognize speech in noise (Meister et al. 2020).

Hypothesis: Stream segregation mediates the relationship between speech recognition in competing speech, auditory resolution and working memory

The premise of this proposal is that individual differences in auditory resolution and cognition affect speech recognition in competing speech directly by affecting recognition of target speech and indirectly by affecting the difficulty of segregating target speech from competing speech. These direct and indirect pathways can be quantified

in a partial mediator model (Baron and Kenny 1986), with stream segregation as the variable that mediates the predictive power of auditory resolution and cognition for speech recognition in competing speech. In this project, we will test whether a partial mediator model describes the relationship between speech recognition in competing speech, stream segregation, and auditory resolution and cognition.

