## Design

### Sample Size and Power Analysis

Our preliminary data described below indicate that the measures of auditory resolution and working memory we use will correlate with sentence recognition accuracy with coefficients of at least  $r = 0.5$ . Replicating correlations of this magnitude in the proposed study with  $\alpha = 0.05$  and  $\beta = 0.80$  would require 29 participants. We do not currently have an estimate of the indirect path effect sizes in the mediator model because the stream segregation task we are proposing is novel. For a mediator analysis, the needed sample size to achieve  $\beta = 0.80$  is at least 34 participants if the relationship between auditory resolution, working memory and stream segregation and the relationship between stream segregation and speech recognition in noise have effect sizes of 0.59 (Fritz and MacKinnon 2010). Larger sample sizes would be needed for smaller effect sizes. The limited timeline for this project makes it infeasible to power the study for smaller indirect path sizes (e.g. 71 participants if both effect sizes are 0.39), so the goal of this pilot project will be to provide an estimate of the magnitude of these effect sizes as a basis for determining feasibility of subsequent work. The mediator analysis will still be conducted, but interpretation of non-significant outcomes will be framed within the statistical power of the available sample.

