### Primary Outcome: Speech recognition in two-talker masking speech

Perceptually Robust English Sentence Test Open-set (PRESTO) sentences (Tamati, Gilbert, and Pisoni 2013) will be presented in quiet and with a two-talker masker at an average target-to-masker ratio of +5 dB. Participants will hear lists 7 and 15 in quiet and 13 and 17 in noise, to limit the impact of cross-list differences in difficulty (Faulkner et al. 2015) on speech recognition accuracy. Performance will be quantified as the percentage of keywords correctly identified across sentences (152 keywords per condition).

For the two-talker masker, PRESTO sentences from unused sentence lists will be concatenated into a running speech stream. Two samples of this running stream will be sampled and superimposed to form the competing speech for each target sentence. Two talkers will be used to maximize the impact of informational masking on speech recognition (Freyman, Balakrishnan, and Helfer 2004). The masking speech will start 0.5 s prior to the target speech and stop 0.5 s after to ensure that participants are given a timing cue to distinguish the masker from the target. The combination of target sentence and maskers will be fixed (“frozen”) across participants to account for fluctuations in the amount of energetic masking that arise from interactions between targets and maskers (Buss et al. 2020). We will fix long-term target-to-masker ratio because that is conventional in speech recognition research. In addition, we will calculate short-term envelope ratio, defined as the proportion of time in which the target speech has a larger instantaneous envelope than the masker for each sentence.

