#### Predictor 2: Working memory

Preliminary data in young adults with normal hearing (Bosen and Doria, in review) demonstrate a link between a three different memory tasks and recognition of vocoded speech in the presence of a speech masker. These results indicate that the ability of young adults with normal hearing to recognize vocoded speech in speech is sensitive to individual differences in storage and processing. Digit span is also associated with vocoded sentence recognition in quiet in individuals with normal hearing (Bosen and Barry 2020).

In contrast, we did not find a relationship between PRESTO sentence recognition accuracy in quiet and digit span performance in 20 listeners with cochlear implants after controlling for auditory resolution ( $r = 0.25$ ,  $p = 0.28$ ). This finding differs from results in young adults with normal hearing listening to vocoded speech, but additional working memory tasks are needed to determine the reason for this difference. In this study, we will use a battery of quick, reliable memory tasks which assess both storage and processing to determine their relative importance when listening in quiet and in competing speech. These tasks include the three tasks shown to be associated with vocoded speech recognition in competing speech:

*Reading Span* (primarily processing) – Participants alternate between judging if sentences are semantically sensible and storing letters in memory. Between 3 and 7 sentence-letter pairs are presented in each trial, after which participants recall the letters in order. The outcome is the total percentage of letters recalled in the correct position (Conway et al. 2005).

*Serial Digit Span* (primarily storage) – Participants hear a list of between 2 and 9 spoken digits presented with one second between stimulus onsets, then verbally repeat them in order (Bosen and Barry 2020; Bosen and Luckasen 2019). The outcome is the total percentage of digits recalled in the correct position.

*Free Recall* (primarily storage) – Participants read a list of 12 monosyllabic words shown for 750 ms with 250 ms between words, then repeat back words as they remember in any order. The outcome is the average number of words recalled from the list.

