### Predictor 3: stream segregation

A sequence of 6 spoken digits alternating in voice pitch (F0) between a high pitch and a low pitch will be presented. Participants will only repeat digits presented with a high pitch, requiring segregation of the two F0 streams. This is analogous to previous sequential streaming studies which used phonemes (David et al. 2017; Gaudrain et al. 2008), but the use of digits makes identification of individual items easier and insensitive to auditory resolution (Bosen and Luckasen 2019; Moberly, Harris, et al. 2017). Recalling 3 digits from each sequence minimizes variability in recall accuracy which arises at longer list lengths (Unsworth and Engle 2006). The number “seven” will be excluded because it is the only disyllabic digit in English, which can affect recall accuracy (Baddeley, Thomson, and Buchanan 1975; Egner, Sütterlin, and Lugo 2016). The sequence will be presented at a rate of 0.5 s per digit onset. This rate of presentation limits the available strategies to facilitate recall, which avoids introducing variance associated with individual differences in memory strategy (Bailey, Dunlosky, and Kane 2008, 2011). Sequential presentation of digits across streams avoids energetic masking that would arise if streams were presented concurrently. Digits spoken by one talker will be manipulated in Praat to have different F0s, thus keeping vocal tract length constant. Digits will alternate between F0 values of 85/200, 120/200, and 150/200 Hz, with the expectation that recall accuracy will increase as the F0 difference increases because the high and low pitch streams will be more segregated. We will also include a baseline condition in which all digits will be presented with an F0 of 200 Hz and participants recall every other digit, starting with the first. This baseline condition is expected to be more difficult than conditions with alternating voice pitches because no segregation cue is available. The difference in recall accuracy between alternating F0 conditions and the baseline condition will be the metric of stream segregation.

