### Step 2: Predict speech recognition accuracy in quiet

We expect both modulation detection thresholds to be significant predictors of sentence recognition accuracy, which will account for approximately half of the variance. We will compare the likelihood of generalized linear regression models which include only modulation detection thresholds against models which also include the memory components identified in step 1 to determine if these memory components are significant predictors of speech recognition in quiet. We will verify that modulation detection thresholds and working memory task performance are not correlated, as we found in participants with cochlear implants ( $r = -0.36$ ,  $r = -0.15$  for spectral and temporal threshold correlations with digit span,  $p > 0.10$ ).

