### Step 3: Test for a mediating relationship of stream segregation for speech recognition in competing speech

We will extrapolate the predictor model for speech recognition in quiet developed in step 2 to the case of speech recognition in competing speech. If the model performs as well for speech in speech as it does for speech in quiet, we would infer that two-talker speech maskers do not introduce meaningful variability into speech recognition outcomes and stop here. If the speech in quiet model is a worse fit, we will add stream segregation to the predictor model and test whether it predicts unique variance in speech recognition accuracy in competing speech. This would demonstrate that stream segregation is a distinct aspect of speech recognition in the presence of competitors. Finally, to complete the mediator analysis we would test whether modulation detection thresholds and memory factors are significant predictors of stream segregation ability.

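### SAP Step 3 infers a distinct role with competitors from a competing-speech model alone; segregation is never modelled in quiet, so specificity to competitors goes untested

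*SAP*

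**What the plan says.** - **Quiet model (SAP Step 2).** "We will compare the likelihood of generalized linear regression models which include only modulation detection thresholds against models which also include the memory components". Segregation is not among the predictors. The protocol's Participants section adds sex to every analysis.
- **Competing speech (SAP Step 3).** The quiet model is carried over to competing speech, and the analysis continues only if it fits less well: "If the speech in quiet model is a worse fit, we will add stream segregation to the predictor model". No criterion for a worse fit is given. If segregation then explains unique variance in competing-speech accuracy, the SAP concludes: "This would demonstrate that stream segregation is a distinct aspect of speech recognition in the presence of competitors".
- **Premise (protocol, Objectives).** Auditory resolution and cognition are held to act partly "indirectly by affecting the difficulty of segregating target speech from competing speech".
- **Metric (protocol, Predictor 3).** "The difference in recall accuracy between alternating F0 conditions and the baseline condition will be the metric of stream segregation".
- **Outcome data (protocol, Primary Outcome).** The sentences "will be presented in quiet and with a two-talker masker at an average target-to-masker ratio of +5 dB", with 152 keywords per condition, so both scores come from the same participants.
- **Memory, for comparison (protocol, Predictor 2).** The memory tasks are used "to determine their relative importance when listening in quiet and in competing speech". No section plans the same for segregation.

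**The concern.** The conclusion speaks of listening with competitors, but the model behind it has one outcome, accuracy in competing speech. Suppose that people who score well on the segregation task also have some general listening ability not captured by thresholds, memory or sex, and that this ability helps equally in quiet and in noise. Segregation would then predict competing-speech accuracy, and the Step 3 sentence would be written, although nothing about competitors was involved. No planned analysis would reveal this.

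The conclusion bears on the study's central hypothesis, and the pilot is meant to guide later work. An association equally present in quiet could be carried forward as one tied to competing speech.

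**Working it through.** **The plan's figure.** The plan attaches no number to this inference. Its nearest figure, 29 participants for r = 0.5, reproduces by Fisher z with two-sided 5% and 80% power: (2.8016 / 0.5493)² + 3 = 29.01. The point does not depend on it.

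**Step 1: why the test cannot separate the two explanations.** Let X be thresholds, memory and sex, G a general ability independent of X with the same effect g in both conditions, and S the standardised segregation score with correlation ρ to G. S has no competitor-specific effect.
- Slope of S given X in competing speech: g × ρ
- Slope of S given X in quiet: g × ρ
- Contrast between conditions: gρ − gρ = 0

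Step 3 tests only the first line.

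**Step 2: worked example.** n = 30 is from the protocol; the other inputs are assumptions. Coefficients are 0.5 and 0.35 (thresholds), 0.3 (memory) and 0.5 (G). Error variance is 0.16, with either 0 or 0.09 added in noise.
- Variance from X: 0.25 + 0.1225 + 0.09 = 0.4625
- Total in quiet: 0.4625 + 0.25 + 0.16 = 0.8725, so R² = 0.53, close to the half that Step 2 expects
- Share of G in the quiet residual: 0.25 / 0.41 = 61%, a strong factor

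Worse fit is read as a lower R² in noise; there are 4,000 runs per cell.

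| ρ | Slope in each condition (0.5ρ) | Significant in noise | Significant in quiet | Step 3 conclusion reached | Contrast rejects |
|---|---|---|---|---|---|
| 0 | 0 | 5% | 5% | 3-4% | 5% |
| 0.3 | 0.15 | 17-21% | 21% | 10-11% | 4-5% |
| 0.6 | 0.30 | 61-70% | 71% | 36-40% | 5% |
| 0.8 | 0.40 | 88-94% | 95% | 47-59% | 5% |

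**Step 3: keyword-level version.** From the documents: n = 30, 152 keywords per condition, and about half the variance explained in quiet. Assumed: quiet log-odds SD of 1, and mean accuracy of about 62% in quiet and 33% in noise. Scores are analysed as empirical logits. Cells give how often the Step 3 conclusion is reached with no competitor-specific role. Column heads give the variance explained by thresholds and memory in quiet / noise.

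| General factor (share of quiet residual; correlation with metric) | Lower R²: 50/35 | Lower R²: 50/50 | R² drop above 0.10: 50/35 | R² drop above 0.10: 50/50 |
|---|---|---|---|---|
| Fully removed by the subtraction (correlation 0) | 4% | 2-3% | 2-3% | 1% |
| Weak (30%; 0.15-0.3) | 5-7% | 3-6% | 4-5% | 2-3% |
| Strong (60-80%; 0.3-0.6) | 10-44% | 10-40% | 7-29% | 4-14% |

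A repeat of the 50/50 case with the lower-R² reading gave 1-6% for no or a weak factor and 9-42% for a strong one. The ranges are not bounds. When the fall to 35% is produced by shrinking the predictor coefficients in noise, the three rows become 4%, 5-10% and 17-74%.

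**Step 4: the contrast, and how it must be fitted.** A t-test on the noise-minus-quiet difference in empirical logits rejects in 4-6% when the factor acts equally in both conditions. The choice of model matters. A binomial mixed model with only a participant intercept leaves no room for participants to differ in their noise-minus-quiet change beyond keyword sampling. In the equal-effect 50/50 case with correlation 0.45 (300 runs per cell), its contrast rejected in 53%, 42% and 28% for factor shares of 30%, 60% and 80%. The difference t-test on the same data rejected in 5-6%. A further check of a contrast allowing only for binomial error gave about 30-54%.

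**The case against.** **The sentence can be read modestly.** Its closing words may simply name the outcome just mentioned, and *distinct* may mean distinct from the predictors already in the model. On that reading the test gives associational support, and mediation in competing speech requires no null result in quiet. This stands in part. The sentence does not state the limit, however, and *demonstrate*, set beside the protocol's premise, invites the competitor-specific reading.

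**The task design protects the metric.** Digits were chosen to depend little on auditory resolution, only three are recalled, the presentation rate limits memory strategies, the streams do not overlap in time, and the same-pitch baseline is subtracted. These features point towards a weak residual factor, and the documents give no evidence of a strong one. This stands, and it lowers the likely size. But the subtraction removes only what affects both digit conditions equally. Pitch sensitivity, for example, would remain, and might also help in quiet.

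**The fit condition protects the inference.** It lowers how often the test is run. A worse fit of the threshold-and-memory model does not show that segregation is irrelevant in quiet.

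**Stronger readings to avoid.** A reader might infer that the SAP claims segregation plays no part in quiet, or that a positive Step 3 result would probably be an artefact. The SAP does not say the first. The second needs effect sizes the protocol lacks: "We do not currently have an estimate of the indirect path effect sizes in the mediator model". Nor are the competing-speech path estimates invalid; a quiet model would leave them unchanged.

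**Conclusion.** The concern holds as a limit on what Step 3 may conclude. A positive result shows association beyond thresholds, memory and sex; specificity to competitors is not tested. This follows from the text and needs no assumed numbers.

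How often the sentence would mislead does depend on assumptions. In the main scenarios it is near or below 5-7% if little general ability survives the digit-task design, and roughly 10-40% only with an assumed strong factor. More extreme choices go higher and a stricter fit criterion goes lower. The design leans towards the low end.

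The matter is worth correcting before analysis, but it does not affect the validity of the data.

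**What to change.** 1. **Reword the Step 3 sentence**, for example: *This would show that stream segregation is associated with recognition in competing speech beyond modulation thresholds, memory and sex; whether the association is stronger than in quiet will be judged from the segregation-by-condition contrast.*
2. **Where Step 3 proceeds past the fit condition, also fit segregation in the quiet model.** Regress each participant's noise-minus-quiet difference in empirical logits on segregation, thresholds, memory components and sex. Report the segregation coefficient with its 95% CI. An equivalent linear mixed model on empirical logits is acceptable. A binomial mixed model must include participant-by-condition (observation-level) variance.
3. **Report the contrast mainly as an estimate**, in keeping with the pilot aim.

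**Cost.** One sentence and one further analysis of data already planned. Precision is limited. In the 50/35 case the CI half-width is about 0.35-0.46 log-odds per SD of segregation, with 39-62% power for a competitor-specific slope of 0.4 and 69-90% for 0.6. A more favourable scaling gave half-widths of 0.22-0.37 and 57-93% power for 0.4.

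Two limits should be stated with the result. A non-significant contrast does not show equal association. A significant one does not exclude a general factor that matters more in harder listening: with a strong factor 1.25 times larger in noise the contrast rejects in 6-9%, and at 1.5 times in 8-41%. The top of that last range is an extreme case, where the factor is 97% of the residual variance in noise.
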